3.2. Adaptive Features and Risk Management of Study Design

The rational of having the following adaptive features is based on the hypothesis-forming approach of this clinical trial. The features from [Table 3-2](#) may be adapted during the study.

Table 3-2. Adaptive Features and Boundaries

Adaptive study design category	Adaptive Features	Boundaries
Dose level for cohorts	Dose levels may be adjusted	Doses are intended to escalate, however, they may be adjusted to higher or lower doses on the basis of safety, tolerability, and PD data reported in the previous cohort(s).

Abbreviations: PD = pharmacodynamic; PK = pharmacokinetic.

Decision-making process for the above adaptive study categories will be as follows:

- Interim review of safety and tolerability of kratom and emerging data (PD) from completed or ongoing cohorts in a blinded fashion by the SRC.
- Outcome on the adaptive study category will be documented by the SRC.

Based on the above, implementation can be performed without delay and Research Ethic Committee approval. If any adaptive features are outside the above pre-specified boundaries, Research Ethic Committee approval is mandatory before implementation.

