1.3. Rationale for Dose Selection

Human abuse potential studies investigate a range of doses from the highest proposed therapeutic dose to supratherapeutic doses (2-3× highest therapeutic dose, if it can be done safely). In order to determine an appropriate kratom dose range for a future human abuse potential study, kratom will first be evaluated in this dose escalation study to examine the safety, tolerability, PK, and PD effects in the intended study population (healthy nondependent recreational polydrug users with opioid experience). Based on published epidemiological papers, doses of kratom used for medical or non-medical purposes range widely from 1 to 12 g. Doses below 6 g are typically considered low doses, whereas doses over 6 g are considered high doses. Doses in excess of 7 to 8 g are considered to produce strong sedation and analgesia effects, whereas lower doses < 5 g are reported as producing stimulant-like effects.⁶ To evaluate the full range of PD effects, up to 5 dose levels will be evaluated starting with a low dose (1 g) and escalating to approximately 8 g to evaluate the pharmacological properties of kratom. Doses may exceed 8 g if it is deemed safe based on interim safety reviews. Doses will be adjusted as needed between cohorts based on review of safety and PD data.

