3. STUDY DESIGN

3.1. Overall Study Design

This single center, single-dose, randomized, adaptive, double-blind, placebo-controlled study will consist of 5 SAD cohorts. A total of 40 healthy, male and female nondependent, recreational polydrug users with opioid experience (8 subjects in each of the 5 cohorts) will be included.

Subjects will only participate in 1 cohort. The planned dose levels by cohort are presented in [Table 3-1](#).

Table 3-1. Sample Dose Levels

Cohort	Number of Subjects (active:placebo)	Dose ^a	Regimen
1	8 (6:2)	1 g (2 capsules)	Single oral administration of kratom or placebo on Day 1
2	8 (6:2)	E.g., 2 g (4 capsules)	
3	8 (6:2)	E.g., 4 g (8 capsules)	
4	8 (6:2)	E.g., 6 g (12 capsules)	
5	8 (6:2)	E.g., 8 g (16 capsules)	

a. Or until the maximum tolerated dose is defined

Dose levels presented are approximations and may be increased or decreased based on interim safety reviews. Doses may be increased, above those shown above in [Table 3-1](#), if there are no safety concerns and if it is deemed that there are minimal effects on PD measures. The upper dose may exceed 8 g if deemed appropriate and safe by interim data reviews.

Subjects will be confined to the clinical site from the day prior to drug administration until 48 hours following drug administration. Subjects will return to the clinical site for a Follow-Up Visit on Day 7 ± 2 . The total duration of the study including Screening will be up to 37 days.

Blood samples for PK assessments will be collected before and over 48 hours after study drug administration. Assessments for the evaluation of PD will be performed before and over 24 hours after study drug administration. Safety and tolerability will be assessed throughout the study.

Following completion of each cohort, a Safety Review Committee (SRC) will review all safety and/or PD data to evaluate progression to the next dose cohort. The SRC will be comprised of the Principal Investigator at the Investigational site, the Study Manager and personnel from the Sponsor's scientific team at a minimum. Dosing of each cohort will be adequately scheduled apart to ensure sufficient time for review of the safety and PD data prior to dosing of the next cohort.

Subjects who terminate the study early will perform End of Study procedures (procedures from the Follow-Up Visit) as soon as possible after the time of Early Termination.

The schedule of activities of the study is described in [Table 6-1](#).

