3.3. Maximum Tolerated Dose

The Maximum Tolerated Dose (MTD) definition: Transient, mild or moderate AEs occurring at a given dose level will be evaluated by the SRC prior to dose escalation. If such AEs occurred in ≥ 3 subjects at a given dose level, dose escalation may be ceased and this dose level or the next lower one will be considered the MTD, or an intermediate dose level can be investigated. If such AEs occurred in ≤ 2 subjects depending on the particular adverse effects observed, the current dose level may be considered the MTD, or dose escalation may proceed.

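### Table 3-2 sets no maximum dose or step, so no dose size can trigger the ethics approval that Protocol 3.2 requires outside its boundaries

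*Protocol*

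**What the plan says.** Protocol 3.2 sets up two routes for changing a dose. Inside the boundaries of Table 3-2, once the SRC has reviewed the blinded data and documented its decision, "implementation can be performed without delay and Research Ethic Committee approval". Outside them, "If any adaptive features are outside the above pre-specified boundaries, Research Ethic Committee approval is mandatory before implementation".

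Table 3-2 has one row, dose level. Its boundary entry says that doses are meant to escalate but that "they may be adjusted to higher or lower doses on the basis of safety, tolerability, and PD data reported in the previous cohort(s".

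The doses in Table 3-1 (1, 2, 4, 6 and 8 g) are headed as samples and described as approximate. Protocol 3.1 allows doses above the table "if there are no safety concerns and if it is deemed that there are minimal effects on PD measures", and then says separately: "The upper dose may exceed 8 g if deemed appropriate and safe by interim data reviews". The synopsis and SAP 3.1 repeat this. Protocol 1.3 says: "Doses may exceed 8 g if it is deemed safe based on interim safety reviews". None of these places gives an upper figure.

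**The concern.** A rule that demands approval outside a boundary needs a boundary that something can cross. The Table 3-2 entry says what kind of evidence must support a change. It does not say how large the change may be. For dose size, the mandatory approval in 3.2 therefore has nothing to act on.

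This matters most above 8 g. Protocol 1.1 and 1.4.1 describe the safety data as limited and the true rate of adverse reactions as hard to establish. Protocol 1.3 associates strong sedation with doses above 7 to 8 g. Subjects in a late cohort could receive a dose well above the listed top without the ethics review that 3.2 presents as the safeguard for changes beyond its limits.

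**Working it through.** The plan states no ceiling, so there is no figure to reproduce. The check is to read each provision that governs dose and ask whether it fixes a maximum dose or a maximum step.

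| Provision | What it controls | Maximum dose? | Maximum step? |
|---|---|---|---|
| Protocol 3.2, Table 3-2 | Basis for a change | No | No |
| Protocol 3.1, synopsis, SAP 3.1 | Sample doses; top may exceed 8 g | No | No |
| Protocol 1.3 | Plan to reach about 8 g; may go higher | No | No |
| Protocol 3.3 (MTD) | Response to adverse events already seen | No | No |
| Protocol 4.3.2.1.2 and 4.3.2.1.3 | Halt after stated events | No | No |
| Protocol 5.3 | Dosing completed within 5 minutes | No | No |
| Protocol 12.2 | IRB route for amendments and consent revisions | No | No |

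No provision supplies either figure, so no dose size lies outside Table 3-2. Protocol 12.2 does not close the gap through the protocol itself: the text already permits doses above 8 g without limit, so a higher dose does not require an amendment.

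**What the text permits.** The inputs are the sample doses in Table 3-1, the 500 mg capsule (5.1.1), and the statement in 1.3 that "doses of kratom used for medical or non-medical purposes range widely from 1 to 12 g".

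- Steps in Table 3-1: 2/1 = 2.0; 4/2 = 2.0; 6/4 = 1.5; 8/6 = 1.33. The largest is 2.0x.
- Repeating 2.0x over five cohorts: 1, 2, 4, 8, 16 g.
- 16 g / 0.5 g = 32 capsules; 16/8 = 2.0 times the sample top dose; 16/12 = 1.33 times the upper end of reported use.

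This schedule crosses no Table 3-2 boundary, provided that the SRC bases each choice on safety, tolerability and PD data.

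**With a 12 g maximum.** 12 g / 0.5 g = 24 capsules, and 12/8 = 1.5 times the sample top dose. Every dose in Table 3-1 lies below it. The 16 g dose would go to the ethics committee first.

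**The case against.** The strongest case on the other side has four parts.

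- **The boundary is not empty.** A reader might infer that no dose increase can ever require ethics approval. The text does not support that. Table 3-2 limits the basis for a change, so an increase made on PK data alone would fall outside it and need approval. The point concerns dose size only.
- **Other safeguards exist.** A reader might infer that escalation is unchecked. It is not. The SRC reviews every cohort and the stopping rules halt dosing after stated events. Footnote a of Table 3-1 ends escalation once the MTD is defined. When 3 or more subjects are affected, Protocol 3.3 also speaks to how far to go: escalation may stop at that level or the next lower one, or an intermediate dose may be studied. What remains is that these rules depend on events. At 2 or fewer affected subjects, "the current dose level may be considered the MTD, or dose escalation may proceed", with no limit on the next dose.
- **There may be a second ethics route.** Subjects are told a dose range (5.2.4), and consent revisions go to an IRB (12.2). If the consent form states an upper dose, exceeding it could bring IRB review. The consent form is not in the documents, so this can be neither relied on nor ruled out. The IRB also approves the protocol, open top included, before the study starts (10.1). That is consent to the wording, but it does not give 3.2 a dose to act on.
- **16 g may be impractical.** Thirty-two capsules in 5 minutes is one every 300/32 = 9.4 seconds, with at most 480/32 = 15 mL of water each. This bears on how likely 16 g is, but 5.3 is not a Table 3-2 boundary. Nor do the documents suggest that the sponsor intends 16 g: 1.3 plans for about 8 g.

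It is also fair to say that 1.1 and 1.3 intend supratherapeutic doses to be studied, so any cap should leave room above 8 g or be open to justification.

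**Conclusion.** The point holds for dose size. Protocol 3.2 promises ethics approval beyond set boundaries, but no dose, however large, lies beyond the boundary that Table 3-2 gives. On the plan's own largest step the text would admit 16 g in cohort 5. That rests on cohort 4 being raised to 8 g and cohort 5 then doubled, each after SRC review. It shows the reach of the wording and is not a prediction.

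Whether the 3.1 condition of minimal PD effects is a firm limit cannot be settled from the text: it is phrased as permission, Table 3-2 does not carry it over, and the next sentence opens the top dose without it.

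This is an inexpensive improvement that should be made. It does not show that subjects are unprotected. Confidence is high that the figure is missing. How much this matters in practice is less certain, because the consent form is unseen.

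**What to change.** Add a numeric maximum dose to Table 3-2 and state that any higher dose goes to the ethics committee first, as 3.2 already requires. An example is 12 g (24 capsules). That is the upper end of reported use in 1.3 and not a safety limit, so the sponsor may justify another figure. Point the sentences in the synopsis, Protocol 1.3 and 3.1 and SAP 3.1 that allow more than 8 g to this maximum, and make the dose range told to subjects (5.2.4) match it.

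A maximum step is optional and for the sponsor to set. If 2.0x is chosen, exempt the doses listed in Table 3-1. Otherwise a downward adjustment could block them: with cohort 2 held at 1 g, the limit for cohort 3 would be 2.0 x 1 = 2 g, below the listed 4 g.

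The cost is wording in two documents, with no added subjects or procedures. The sponsor would need ethics approval before exceeding the stated maximum. All five doses in Table 3-1 remain available and, with 12 g as the example, so does room up to 1.5 times the sample top dose.

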3.3. Maximum Tolerated Dose

The Maximum Tolerated Dose (MTD) definition: Transient, mild or moderate AEs occurring at a given dose level will be evaluated by the SRC prior to dose escalation. If such AEs occurred in ≥ 3 subjects at a given dose level, dose escalation may be ceased and this dose level or the next lower one will be considered the MTD, or an intermediate dose level can be investigated. If such AEs occurred in ≤ 2 subjects depending on the particular adverse effects observed, the current dose level may be considered the MTD, or dose escalation may proceed.

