4.3.2.1.2. Cohort Stopping Rules

If any of the following safety concerns are observed, dosing of all subjects at the given dose level or higher will be suspended/halted and all available data will be evaluated by the SRC. Dose continuation (remaining subjects within a cohort or remaining dosing for a subject) or escalation should not proceed for any of, but not limited to, the following reasons:

- If 1 kratom-related SAE occurs in a cohort
- Moderate or severe AEs in 50% of the subjects in the cohort or more

Dose escalation will be discussed during the SRC meeting and may be stopped depending on Principal Investigator's or Sponsor's decision.

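### The MTD count leaves out severe AEs, and the only mandatory count that includes them needs 4 of 8 subjects, so up to 3 severe non-serious cases can require neither a within-cohort pause nor an MTD decision

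*Protocol*

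**What the plan says.** Section 3.3 of the protocol opens its MTD definition with "Transient, mild or moderate AEs occurring at a given dose level will be evaluated by the SRC prior to dose escalation". Two branches follow, both counting AEs of that kind. With 3 or more affected subjects, "dose escalation may be ceased and this dose level or the next lower one will be considered the MTD", or an intermediate dose may be studied. With 2 or fewer, the SRC may either declare the MTD or escalate. Both branches are permissive, and neither mentions severe AEs. The MTD matters because it ends escalation: footnote a to Table 3-1 reads "Or until the maximum tolerated dose is defined".

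The binding rules are in section 4.3.2.1.2. If one is met, "dosing of all subjects at the given dose level or higher will be suspended/halted", and the SRC evaluates the data. The section adds "Dose continuation (remaining subjects within a cohort or remaining dosing for a subject) or escalation should not proceed", so the rule acts within a cohort as well as between cohorts. It lists two triggers: "If 1 kratom-related SAE occurs in a cohort" and "Moderate or severe AEs in 50% of the subjects in the cohort or more". The list is expressly open-ended. The trial stopping rules in 4.3.2.1.3 need 2 kratom-related SAEs in a cohort or 1 attributable death.

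Each cohort has 6 kratom and 2 placebo subjects (sections 3.1 and 5.2.3), and interim review is done "in a blinded fashion by the SRC" (section 3.2). Severity is graded by CTCAE (section 7.2). Seriousness is defined separately, by outcome (section 7.1). The SAP adds no MTD or stopping rule; its section 12 only repeats that blinded data are reviewed after each dose level.

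**The concern.** Safety and tolerability are the primary objective, and control of escalation is the main protection for subjects. An MTD definition would be expected to say what follows from the worst tolerability events. This one names only the milder ones.

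The stopping rules do not clearly fill the hole. One trigger depends on seriousness, which is not the same as severity. The other pools moderate and severe AEs and needs half the cohort, with two subjects in the denominator who received no drug. Section 1.1 anticipates vomiting, and section 1.4.1 lists agitation and hallucinations among reported reactions. Such events can be severe without being judged serious. If 2 or 3 subjects in a cohort have them, nothing written requires dosing of any remaining subjects in that cohort to pause, and nothing says what the events imply for the MTD.

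**Working it through.** The plan gives no operating characteristics for these rules, so there is no figure to reproduce.

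**Step 1. The threshold.** 0.50 × 8 = 4 subjects. Three of 8 is 37.5%, below the trigger, although 3 of the 6 on kratom is 50%. If only kratom subjects are affected, the rule needs 4 of 6, or 67%.

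**Step 2. Which rule reaches severe, non-serious AEs in 1 to 3 subjects?**

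| Rule | Counts severe non-serious AEs? | Binding? |
|---|---|---|
| 3.3, 3 or more subjects | No: transient, mild or moderate only | No |
| 3.3, 2 or fewer subjects | No: same AEs | No |
| 4.3.2.1.2, one kratom-related SAE | No: needs seriousness | Yes |
| 4.3.2.1.2, 50% of the cohort | Yes, but needs 4 of 8 | Yes |
| 4.3.2.1.3, two SAEs or one death | No | Yes |
| SRC review after each cohort, 3.1 | All safety data are open to review, but no outcome is prescribed | The review is; the outcome is not |

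The severe cases can bring about a mandatory suspension only if enough other subjects have moderate or severe AEs to make up 4 of 8. The 3.3 count may be reached separately through other subjects' milder AEs, but it is a prompt between cohorts and does not suspend dosing.

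**Step 3. How often do moderate AEs in others make up the difference?** Take k severe kratom subjects. Let M be the number with a moderate AE among the other 6 − k kratom and 2 placebo subjects, treated as independent. The rule is missed when M ≤ 3 − k. The documents give no AE rates, so the rates below are assumptions (kratom / placebo).

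- k = 3 at 20% / 10%: P(M = 0) = 0.8³ × 0.9² = 0.415.
- k = 2 at 20% / 10%: P(M ≤ 1) = 0.8⁴ × 0.9² + 4 × 0.2 × 0.8³ × 0.9² + 0.8⁴ × 2 × 0.1 × 0.9 = 0.332 + 0.332 + 0.074 = 0.737.

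| Moderate-AE rates | 3 severe | 2 severe | 1 severe |
|---|---|---|---|
| 0 / 0 | 1.000 | 1.000 | 1.000 |
| 10% / 5% | 0.658 | 0.918 | 0.984 |
| 20% / 10% | 0.415 | 0.737 | 0.899 |
| 40% / 20% | 0.138 | 0.346 | 0.548 |

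Each entry is the chance that the 4-of-8 rule is not met, given that many severe cases. It is not the chance that such cases occur.

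**Step 4. False alarms from a threshold of 2.** Suppose each of the 8 subjects has a background chance p of a severe AE judged drug-related. Then P(2 or more) = 1 − (1 − p)⁸ − 8p(1 − p)⁷.

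- p = 2%: 1 − 0.8508 − 0.1389 = 0.0103 per cohort. Over five cohorts: 1 − 0.9897⁵ = 0.051.
- p = 5%: 1 − 0.6634 − 0.2793 = 0.0572 per cohort. Over five cohorts: 0.255.

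A threshold of 1 would give 14.9% per cohort at 2% and 33.7% at 5%.

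**The case against.** The strongest reply is that oversight does not depend on these counts. Section 3.1 requires SRC review after every cohort and spaces dosing to allow it, and section 3.2 has the outcome documented. The suspension list is open-ended, and escalation may be stopped by the investigator or the sponsor. This stands. A reader might infer that the next cohort could be dosed after several severe AEs without any pause, but section 3.1 rules that out. What discretion does not supply is a required pause for subjects not yet dosed in the current cohort, or a stated MTD consequence.

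Second, the SAE route may catch some of these events. Section 7.1 includes important medical events on the investigator's judgement, so severe agitation or hallucinations might qualify, and one kratom-related SAE halts dosing. This also stands. How often an AE would be severe but not serious cannot be established from the documents.

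Third, a within-cohort pause helps only if some subjects are still undosed. No sentinel or staggered dosing is described. The wording of 4.3.2.1.2 contemplates remaining subjects, but the practical gain depends on a schedule the protocol does not give.

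Fourth, two readings would narrow the gap. If transient is a category of its own in 3.3, only lasting severe AEs are left out there. If the 50% applies to subjects dosed so far, the threshold is lower in mid-cohort: 2 of 4, or 3 of 5 or 6. The text settles neither.

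A reader might also infer that the plan is stricter on mild AEs than on severe ones. That goes too far: the 3.3 count is permissive, and the binding rule ignores mild AEs.

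**Conclusion.** The gap is real on the text and should be closed. Severe AEs not judged serious in up to 3 of 8 subjects, including 3 of 6 on kratom, are not counted toward the MTD. They meet no written suspension criterion unless moderate AEs in others bring the total to 4.

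Given 3 such cases, the rule is missed in 41% of cohorts at assumed moderate-AE rates of 20% and 10% (range 14% to 100% over the rates tried). Given 2, it is 74% (35% to 100%). These figures assume independent subjects and a full cohort of 8, with the whole cohort as denominator. The finding follows from the wording; the percentages only illustrate it.

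The consequence is limited. The documents do not support saying that severe AEs go unreviewed. What is missing is a mandatory within-cohort pause and an MTD outcome. I would ask for the change with medium confidence.

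**What to change.** (a) In 3.3, state that AEs of any severity are evaluated and counted. Add that severe drug-related AEs in 2 or more subjects require a documented SRC decision: the next lower dose is the MTD, an intermediate dose is studied, or escalation resumes with reasons given.

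(b) Add a bullet to 4.3.2.1.2: dosing is suspended pending blinded SRC review when 2 or more subjects in the cohort have severe AEs with a reasonable possibility of relation to study drug, as defined in Table 7-1.

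A single severe non-serious AE stays with SRC discretion. The sponsor should confirm the threshold of 2. With 6 exposed, it is met in 11%, 34% and 58% of cohorts at true severe rates of 10%, 20% and 30%. A threshold of 1 is met in 47%, 74% and 88%, but with far more false alarms.

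The cost is one bullet and two sentences, with no extra subjects, visits or data. The downside is an occasional needless pause on a blinded count that may include placebo subjects: 1.0% of cohorts and 5.1% of five-cohort trials at a 2% background rate, or 5.7% and 25.5% at 5%. Each is a pause for review, after which dosing may resume.

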4. SUBJECT POPULATION

Subjects meeting all the inclusion criteria and none of the exclusion criteria at Screening may be eligible for participation in this study. Continued eligibility will be assessed upon admission to the clinical site, prior to study drug administration.

Screen failures are defined as participants who consent to participate in the clinical trial but are not subsequently randomly assigned to the study intervention or entered in the study.

